4.2 STUDY ENDPOINTS

4.2.1 PRIMARY ENDPOINT

The primary endpoint is time to TKI treatment discontinuation due to progressive disease, intolerability (Grade 3 and 4 toxicities refractory to best symptom management that are deemed probably or definitely related to study treatment only), or disease-related death at 2 years. We hypothesize that time on TKI treatment will be significantly longer for patients on the adaptive therapy arm than on the conventional therapy arm because we expect a decrease in drug-associated toxicities and a delay in the selection of resistant clones in the adaptive therapy arm.

4.2.2 SECONDARY ENDPOINTS

We will evaluate overall response rate, progression free survival and overall survival of the adaptive therapy regimen and of the conventional therapy regimen.

4.2.3 EXPLORATORY ENDPOINTS

We will determine predictive biomarkers of TKI response.

5. STUDY ENROLLMENT AND WITHDRAWAL

5.1 PARTICIPANT INCLUSION CRITERIA

Subjects who meet all inclusion criteria will be able to participate in the study.

Inclusion criteria:

1. All histologically or cytologically confirmed diagnosis of thyroid cancer, other than anaplastic or stromal-cell derived cancers.
2. **Participants with DTC** must have negative thyroglobulin antibodies.
3. Measurable disease meeting the following criteria and confirmed by central radiographic review:
 - At least 1 lesion of ≥ 1.0 centimeter (cm) in the longest diameter for a non- lymph node or ≥ 1.5 cm in the short-axis diameter for a lymph node which is serially measurable according to Response Evaluation Criteria in Solid Tumors (RECIST) 1.1 using computerized tomography/magnetic resonance imaging (CT/MRI). If there is only one target lesion and it is a non-lymph node, it should have a longest diameter of ≥ 1.5 cm.
 - Lesions that have had external beam radiotherapy (EBRT) or locoregional therapies such as radiofrequency (RF) ablation must show evidence of progressive disease (substantial size increase of $\geq 20\%$) within 12 months to be deemed a target lesion.
4. Participants must show evidence of disease progression comparing (a) scan in screening and (b) historical scan obtained within 12 months prior to signing informed consent, according to RECIST 1.1 assessed and confirmed by central radiographic review of CT and/or MRI scans.
5. **Participants with DTC** must not be eligible for possible curative surgery and must be radioiodine (RAI)-refractory / resistant as defined by at least one of the following:
 - One or more measurable lesions that do not demonstrate iodine uptake on any

- radioiodine scan
 - One or more measurable lesions that has progressed by RECIST 1.1 within 12 months of RAI therapy, despite demonstration of radioiodine avidity at the time of that treatment by pre- or post-treatment scanning.
 - Disease progression in a patient that has received a cumulative activity of RAI of ≥ 550 millicuries (mCi) (22 gigabecquerels), with the last RAI dose administered at least 6 months prior to study entry.
 - Otherwise deemed not a candidate for further RAI therapy by a multidisciplinary tumor board within 60 days of enrollment
6. **Participants with DTC** must be receiving thyroxine suppression therapy and thyroid stimulating hormone (TSH) should not be elevated (TSH should be ≤ 0.1 mU/L).
 7. “Measurable” tumor marker (non-stimulated thyroglobulin >10 ng/mL in patients with DTC; or serum basal calcitonin >10 pg/mL or CEA > 10 ng/mL in patients with MTC)
 8. Participants may have received prior multi-kinase targeted therapy except the TKI used in this trial. For example, patients getting Lenvatinib on this study may have been previously treated with Sorafenib, Vandetanib, Sunitinib, Pazopanib, etc. Each of the TKI targeted agents will be counted individually, regardless of the duration of its administration.
 9. Participants with known brain metastases who have completed whole brain radiotherapy, stereotactic radiosurgery or complete surgical resection, will be eligible if they have remained clinically stable, asymptomatic for 30 days.
 10. All chemotherapy or radiation related toxicities must have resolved to $<$ Grade 2 severity per Common Terminology Criteria for Adverse Events (CTCAE v 5.0), except alopecia, infertility, anemia (see separate criteria) and any toxicities deemed irreversible by the treating physician.
 11. Participants must have an Eastern Cooperative Oncology Group (ECOG) Performance Status of 0 – 2 (See Appendix 2).
 12. Adequately controlled blood pressure (BP) with or without antihypertensive medications, defined as BP $\leq 150/90$ mm Hg at screening and no change in antihypertensive medications within 1 week prior to Cycle 1/Day 1
 13. Adequate renal function defined as calculated creatinine clearance ≥ 30 mL/min (using Cockcroft/Gault formula)
 14. Adequate bone marrow function:
 - Absolute neutrophil count (ANC) ≥ 1500 mm³ ($\geq 1.5 \times 10^3$ /micro liter [μ L])
 - Platelets $\geq 100 \times 10^9$ / L
 - Hemoglobin ≥ 9.0 g/dL
 - Adequate blood coagulation function as evidenced by an INR ≤ 1.5
 15. Adequate liver function:
 - Bilirubin $\leq 1.5 \times$ upper limit of normal (ULN) except for unconjugated hyperbilirubinemia or Gilbert's syndrome who must have a total bilirubin level of $< 3.0 \times$ ULN).
 - Alkaline phosphatase, alanine aminotransferase (ALT), and aspartate aminotransferase (AST) $\leq 3 \times$ ULN ($\leq 5 \times$ ULN if participant has liver metastases).
 16. Males or females age ≥ 18 years at the time of informed consent
 17. Females must not be breastfeeding or pregnant at Screening or Baseline (as documented by a negative human chorionic gonadotropin [hCG]). A separate baseline assessment is required if a negative screening pregnancy test was obtained more than 72 hours before the first dose of study drug.
All females will be considered to be of childbearing potential unless they are postmenopausal (amenorrhea for at least 12 consecutive months, in the appropriate age group, and without other known or suspected cause) or have been sterilized surgically

- (ie, bilateral tubal ligation, total hysterectomy, or bilateral oophorectomy, all with surgery at least 1 month before dosing).
18. Females of childbearing potential must not have had unprotected sexual intercourse within 30 days prior to study entry and must agree to use a highly effective method of contraception (e.g., total abstinence, an intrauterine device, a double-barrier method [such as condom plus diaphragm with spermicide], a contraceptive implant, an oral contraceptive, or have a vasectomized partner with confirmed azoospermia) throughout the entire study period and for 30 days after study drug discontinuation. If currently abstinent, the participant must agree to use a double-barrier method as described above if she becomes sexually active during the study period or for 30 days after study drug discontinuation. Females who are using hormonal contraceptives must have been on a stable dose of the same hormonal contraceptive product for at least 4 weeks prior to dosing and must continue to use the same contraceptive during the study and for 30 days after study drug discontinuation.
 19. Male participants must have had a successful vasectomy (confirmed azoospermia) or they and their female partners must meet the criteria above (ie, not of childbearing potential or practicing highly effective contraception throughout the study period and for 30 days after study drug discontinuation). Those with partners using hormonal contraceptives must also be using an additional approved method of contraception, as described previously.
 20. Voluntary agreement to provide written informed consent and the willingness and ability to comply with all aspects of the protocol

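### The cumulative radioiodine cut-off in inclusion criterion 5 pairs 550 mCi with 22 GBq, but 550 mCi is 20.35 GBq, so the two units set different cut-offs for that one route

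*Combined protocol and SAP*

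**What the plan says.** Criterion 5 in Section 5.1 applies to participants with DTC only. They "must not be eligible for possible curative surgery and must be radioiodine (RAI)-refractory / resistant". The refractory part of the criterion is met in any of several ways: "radioiodine (RAI)-refractory / resistant as defined by at least one of the following". Four routes follow:

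1. at least one measurable lesion without iodine uptake;
2. a measurable lesion that took up iodine but progressed within 12 months of radioiodine treatment;
3. progression after a stated total of radioiodine, with a minimum interval since the last dose;
4. a tumor board judgement: "Otherwise deemed not a candidate for further RAI therapy by a multidisciplinary tumor board within 60 days of enrollment".

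The total in the third route is written as "cumulative activity of RAI of ≥ 550 millicuries (mCi) (22 gigabecquerels", with the GBq figure in parentheses after the mCi figure. From the number 550 on, the wording runs "millicuries (mCi) (22 gigabecquerels), with the last RAI dose administered at least 6 months prior to study entry". The protocol does not call the GBq figure approximate, does not name a governing unit, and does not repeat the threshold elsewhere in the text available.

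**The concern.** A threshold written in two units should be one threshold. The millicurie and the gigabecquerel are linked by a fixed definition, so the figure in parentheses can be checked exactly, and it fails the check. This matters more than a slip in background text because the number sits in an operative inclusion criterion, and Section 5.1 requires participants to meet all of these. Section 9 also provides for monitoring of source data and of adherence to the protocol. If a patient's past treatment is recorded in GBq and compared with 22, the answer for this route can differ from the one obtained by comparing the same activity in mCi with 550. At stake is whether a patient in the band between the two figures satisfies this route.

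**Working it through.** **Inputs**

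- Threshold in mCi: 550 (Section 5.1, criterion 5, third route).
- Threshold in GBq: 22 (same place).
- Conversion: 1 Ci = 3.7 × 10^10 Bq, so 1 mCi = 0.037 GBq. The protocol does not state this. It is a unit definition, not an assumption about the trial.

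**Attempt to reproduce the plan's figure**

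GBq = mCi × 0.037 = 550 × 0.037 = 20.35 GBq. The stated 22 GBq is not reproduced.

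**Reverse conversion**

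mCi = GBq / 0.037 = 22 / 0.037 = 594.6 mCi.

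**Size of the gap**

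- In GBq: 22 − 20.35 = 1.65.
- In mCi: 594.6 − 550 = 44.6.
- Relative: 1.65 / 20.35 = 8.1%. On the other base, 1.65 / 22 = 7.5%.

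**Can rounding explain it?**

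- 550 mCi rounded to a whole number of GBq is 20, not 22.
- If 22 GBq is itself a rounded value, it stands for 21.5 to 22.5 GBq, which is 21.5 / 0.037 = 581 mCi to 22.5 / 0.037 = 608 mCi. That range excludes 550.
- A coarse factor of 0.04 GBq per mCi gives 550 × 0.04 = 22.0. This may be how the figure arose, but 0.04 / 0.037 = 1.081, so the factor is 8.1% too high and does not make the two values equal.

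**Who is affected**

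For a DTC patient who satisfies the third route's other conditions (progression and the interval since the last dose):

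| Cumulative activity | Route read in mCi | Route read in GBq |
|---|---|---|
| Below 550 mCi (below 20.35 GBq) | not met | not met |
| 550 to just under 594.6 mCi (20.35 to just under 22 GBq) | met | not met |
| 594.6 mCi or more (22 GBq or more) | met | met |

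Only the middle row depends on the unit. Even there, criterion 5 is still satisfied in either unit if any of the other three routes applies. Eligibility as a whole changes only for a patient in the middle row who meets none of them.

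**The case against.** The strongest reply accepts the arithmetic and disputes the consequence. The at-least sign is attached to the mCi figure. The GBq figure stands in parentheses with no operator of its own and reads as a conversion aid. Staff who follow the sentence as written would apply 550 mCi. There is one enrolling site (Study Summary), so sites cannot diverge in the unit they use. The tumor board route carries no activity threshold and could admit any patient in the gap.

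Most of this stands. It disposes of three stronger conclusions that a reader might infer:

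- **That the criterion cannot be applied or audited consistently.** The sentence has a natural reading under which it can be applied. What remains is that the protocol does not state that reading and gives an incorrect equivalent beside it.
- **That a patient's eligibility in general depends on the unit.** Only one sub-criterion out of four alternatives does.
- **That the error threatens the trial's comparison.** Criterion 5 is applied before treatment. Randomization comes later, after the tumor marker has fallen by at least 50% (Sections 4.1 and 7.3.3), so the criterion acts equally on both arms. It does not enter the endpoint, the alpha, or the sample-size and power statements in Sections 10.1 and 10.4. Participants with medullary cancer are outside its scope.

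The reply does not remove the mismatch itself. Nothing elsewhere in the protocol corrects either figure or says which one governs.

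**Conclusion.** The point holds as a minor correction to an eligibility threshold. The two figures differ by 1.65 GBq, or 44.6 mCi, and the cut-off of the third route depends on which is read. The number of patients whose overall eligibility would change cannot be derived. The documents give neither a distribution of cumulative radioiodine activity nor a count of patients who would rely on this route alone. Even a statement that few are affected would be an inference, and the number may be zero.

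The conclusion rests on the unit definition and on both numerals being printed as they appear in the text reviewed. A misread numeral cannot be excluded from the text alone, though nothing points to one. The documents do not show which figure was intended, and this review takes no position on that.

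**What to change.** Reconcile the two figures in the third route of criterion 5 so that they express the same activity, with the clinical team confirming which was intended. It would help to state which unit governs, or to give the threshold in one unit only. This is a one-number edit. It changes nothing in the design, the analysis or the sample size. If patients have already been enrolled through this route, a check of whether any fell between 550 and 594.6 mCi without meeting another route would show whether the discrepancy ever mattered.

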- Patients in the adaptive therapy regimen will receive TKI therapy in cycles: continuous treatment at the indicated dose until the patients' tumor marker (thyroglobulin in DTC patients; calcitonin or CEA in MTC patients) drops by $\geq 50\%$ from the level at the time of enrollment ("baseline" level). Only tumor markers that meet inclusion criteria at baseline can be used for randomization and adaptive therapy purposes. A new cycle of TKI treatment will begin:
 - - When/if the tumor marker increases to $\geq 70\%$ of the "baseline" level.
OR
 - At the discretion of the treating physician if a patient develops worsening disease-related symptoms with rising tumor marker levels indicating disease progression. In the case of resumption for disease-related symptoms, TKI treatment will continue until the symptoms improve at the discretion of the treating physician and the tumor markers are again $\leq 50\%$ from the level at the time of enrollment.

Study Duration: 48 months

Participant Duration: 48 months

SCHEMATIC OF STUDY DESIGN

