All study participants will be followed for at least 24 months after treatment initiation. Patients will continue to receive treatment until confirmed disease progression, development of unacceptable toxicity, withdrawal of consent, or study termination by investigator. After disease progression, subjects will be followed for survival and may be treated according to standards of care, which includes conventional (continuous) TKI treatment for patients in the adaptive therapy arm.

After 24 months, patients in the adaptive therapy arm that remain on TKI therapy and under control will be given the choice to continue with adaptive therapy or to convert to conventional (continuous) regimen, which is the current standard of care.

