Permanently discontinue Cabozantinib for any of the following:

- Development of visceral perforation or fistula formation
- Severe hemorrhage
- Serious arterial thromboembolic event (e.g., myocardial infarction, cerebral infarction)
- Nephrotic syndrome
- Malignant hypertension, hypertensive crisis, persistent uncontrolled hypertension despite optimal medical management
- Osteonecrosis of the jaw
- Reversible posterior leukoencephalopathy syndrome

In Patients Concurrently Taking a Strong CYP3A4 Inhibitor:

Reduce the daily Cabozantinib dose by 40 mg (for example, from 140 mg to 100 mg daily or from 100 mg to 60 mg daily). Resume the dose that was used prior to initiating the CYP3A4 inhibitor 2 to 3 days after discontinuation of the strong inhibitor.

In Patients Concurrently Taking a Strong CYP3A4 Inducer:

Increase the daily Cabozantinib dose by 40 mg (for example, from 140 mg to 180 mg daily or from 100 mg to 140 mg daily) as tolerated. Resume the dose that was used prior to initiating the CYP3A4 inducer 2 to 3 days after discontinuation of the strong inducer. The daily dose of Cabozantinib should not exceed 180 mg

Dose Reduction and Interruption Instructions for Vandetanib

For treatment-related adverse reactions:

The 300 mg daily dose can be reduced to 200 mg (two 100 mg tablets) and then to 100 mg for Common Terminology Criteria for Adverse Events (CTCAE) Grade 3 or greater toxicities.

Interrupt Vandetanib for the following:

- Corrected QT interval, Fridericia (QTcF) greater than 500 ms: Resume at a reduced dose when the QTcF returns to less than 450 ms.
- CTCAE Grade 3 or greater toxicity: Resume at a reduced dose when the toxicity resolves or improves to CTCAE Grade 1.

For recurrent toxicities:

Reduce the dose of Vandetanib to 100 mg after resolution or improvement to CTCAE Grade 1 severity, if continued treatment is warranted.

Because of the 19-day half-life, adverse reactions including a prolonged QT interval may not resolve quickly. Monitor appropriately.

For patients with renal impairment:

Reduce the starting dose to 200 mg in patients with moderate (creatinine clearance ≥ 30 to < 50 mL/min) and severe (creatinine clearance < 30 mL/min) renal impairment.

For patients with hepatic impairment:

Vandetanib is not recommended for use in patients with moderate and severe hepatic impairment.

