7.3.4 FINAL STUDY VISIT

Final Study Visit

At the end of the study (at least 24 months after TKI initiation) the following data will be collected:

- Obtain vital signs.
- Record all concomitant medication use.
- Perform a comprehensive physical examination.
- Evaluate ECOG performance status.
- Obtain laboratory tests and urinary dipstick.
- Obtain thyroid panel (if not done within previous 3 weeks)
- Assess for AEs and SAEs.
- Assess compliance with the medication.
- Diagnostic imaging of affected and suspected sites (CT and/or MRI).
- Assess survival.

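### One 30-day contraception interval for all four TKIs leaves about a third of the last vandetanib level where it governs, and the study period that might extend it is undefined

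*Combined protocol and SAP*

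**What the plan says.** Criterion 18 in Section 5.1 obliges women of childbearing potential to use highly effective contraception "throughout the entire study period and for 30 days after study drug discontinuation". The same 30 days appears in three other places in that section:

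- currently abstinent women must use a double-barrier method "if she becomes sexually active during the study period or for 30 days after study drug discontinuation";
- users of hormonal contraceptives "must continue to use the same contraceptive during the study and for 30 days after study drug discontinuation";
- under criterion 19, men without a confirmed vasectomy and their partners must meet the same standard, which includes "practicing highly effective contraception throughout the study period and for 30 days after study drug discontinuation".

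None of these distinguishes between lenvatinib, sorafenib, cabozantinib and vandetanib. The vandetanib instructions in Section 6.1.8.2 do recognise slow elimination, but only for toxicity: "Because of the 19-day half-life, adverse reactions including a prolonged QT interval may not resolve quickly".

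The term *study period* is not defined. Several durations could be meant:

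- Section 4.1: "All study participants will be followed for at least 24 months after treatment initiation".
- Section 7.3.4: "At the end of the study (at least 24 months after TKI initiation) the following data will be collected".
- Study Summary: "Participant Duration: 48 months".
- Section 5.4.2: survival follow-up for one year after early withdrawal or termination.
- Sections 6.1.8 and 7.3.3: treatment past 24 months is outside the protocol.

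**The concern.** The protocol requires contraception because of exposure to the study drug, so the post-drug interval should bear some relation to how long the drug persists. For vandetanib, the only one of the four agents whose half-life is stated, 30 days is fewer than two half-lives. A site that follows the criterion as written could release a participant or partner from contraception while a material share of the drug is still present.

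Little else in the plan would compensate. Table 8 schedules pregnancy tests only at screening and baseline. Section 8.4.5 covers the reporting of a pregnancy, not its prevention. What is at stake is participant safety; no statistical result depends on it.

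**Working it through.** **Inputs.** Post-drug interval: 30 days (Section 5.1, criteria 18 and 19). Vandetanib half-life: 19 days (Section 6.1.8.2). The plan states no residual-drug figure, so there is nothing of its own to reproduce.

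**Formula.** Under single-phase first-order elimination, the share of the last-dose level left after *t* days is 0.5^(t/19).

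**At day 30.** 30/19 = 1.58 half-lives, and 0.5^1.58 = 0.335, or 33.5%. If the half-life was rounded from anywhere between 18.5 and 19.49 days, the range is 32.5% to 34.4%.

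**When the 30-day limit governs.** The criterion joins the two requirements with *and*, so the later date ends the duty. There are three readings of the study period.

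(a) It ends with treatment. The 30-day limit governs for everyone who stops vandetanib, and 33.5% remains.

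(b) It ends 24 months after TKI start (730.5 days, 30.44 days per month). Days off drug when the duty ends = max(730.5 − stop day, 30).

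| Stop at | Days off drug when duty ends | Share remaining |
|---|---|---|
| Month 20.9 (730.5 − 95 = day 635.5) | 95 | 3.1% |
| Month 21 | 91.3 | 3.6% |
| Month 22 | 60.9 | 10.9% |
| Month 23 | 30.4 | 32.9% |
| Month 24 | 30 | 33.5% |

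The 30-day limit takes over after day 730.5 − 30 = 700.5, that is, month 23.0.

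(c) It includes the one-year follow-up after early withdrawal, or is the 48-month participant duration. At 365 days off drug the share is 0.0000016. For a stop at month 24 with the duty running to month 48 (730.5 days) it is 2.7 × 10⁻¹². There is no gap for those covered. The one-year follow-up applies to patients who stop early, so it would not by itself cover a stop at month 24.

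**Adaptive arm.** For a patient removed during a planned pause, 33.5% is an upper figure if the 30 days are counted from removal. After one 28-day cycle off drug, 28 + 30 = 58 days have passed and 0.5^(58/19) = 12.1%.

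**Longer intervals.**

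| Days after last dose | Share remaining | Extra days over 30 |
|---|---|---|
| 90 | 3.8% | 60 |
| 95 (5 × 19) | 3.1% | 65 |
| 120 | 1.3% | 90 |

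**The case against.** The strongest reply is that the 33.5% depends mainly on the reading with the least textual support. Section 7.3.5 has its own term for the 24-month treatment period, Section 7.3.4 places the end of the study at 24 months or later, and the Study Summary gives 48 months. A patient who stops at month 22 or 23 has stopped early and enters the one-year follow-up of Section 5.4.2. If that follow-up counts as study period, the gap in reading (b) shrinks to those who stop at month 24 itself, and some of those may continue vandetanib off trial. No document gives an acceptable residual, so 95 days is not derived from the protocol. The percentage is relative to each patient's last-dose level, and the dose may already have been reduced to 200 or 100 mg. The consent form, where drug-specific instructions might sit, and parts of Section 7 were not available.

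Most of this stands as a limit on reach: the subgroup is small, possibly empty, and its size depends on an undefined term. It does not remove the gap. If the study period were 48 months, the 30-day clause could not govern for anyone who stops on protocol and stays in the study, which is hard to square with its appearing four times. The End of Treatment visit (Section 7.3.5) and the on-treatment adverse-event window (Section 8.4.1) are also set at 30 days after the last dose, so a site could readily take day 30 as the end of the duty. Patients who stop vandetanib at month 24 also remain exposed under reading (b).

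**Conclusion.** The concern holds. One 30-day interval is applied to all four TKIs. Where it governs, about a third of the last-dose vandetanib level remains when the duty ends, and the plan does not settle when it governs. The result rests on the protocol's own 19-day half-life and single-phase first-order elimination. It shows residual exposure, not a measured fetal risk, and does not by itself establish the correct interval. It is confined to vandetanib, since the protocol gives no half-life for the other three drugs. Those affected are MTC patients of reproductive potential, and their partners, when vandetanib is stopped on protocol; their number is not stated. No available section sets a longer vandetanib interval.

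**What to change.** In all four places in Section 5.1, keep 30 days as the general rule and add: *and, for vandetanib, until at least 95 days after the final vandetanib dose (a planned adaptive-arm pause is not a final dose), or longer if the product labelling requires it*. The 95 days is five half-lives, an assumed convention, and the sponsor should confirm the length against the labelling. State whether the study period ends with treatment, at 24 months, after the one-year follow-up or at 48 months. Align the consent form if it repeats the 30 days.

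The cost is eligibility wording, possibly consent wording, and up to 65 more days of contraception for a few participants and partners (60 if 90 days is chosen, 90 if 120). Sample size, endpoint and analysis are untouched.
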